7.3. Randomization Assignment: Acoustic Enhancer with Ureteroscopic Laser Lithotripsy (Investigational Arm) vs. Standard Ureteroscopic Laser Lithotripsy (Control Arm)

Following consent and if a subject meets the study's inclusion/exclusion criteria, the subject will be randomly assigned to the investigational or control arm on the day of the procedure. If the potential subject does not meet the study procedure eligibility criteria, he/she will NOT be randomly assigned to treatment or the control arm. Random assignment will be conducted using an allocation ratio of 1:1 with one subject randomized to the Investigational Arm for each subject randomized to the Control Arm. Random assignment will be conducted block design generated separately for each clinical site. Subjects will be blinded to treatment allocation through index procedure.

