Subjects may voluntarily withdraw from the study at any time for any reason. The Investigator(s) may elect at any time to withdraw a subject from the study for any reason unrelated to the study treatment if such a decision is in the subject's best medical interest. If a subject discontinues the study, or is withdrawn by the Investigator(s), as much follow-up data as possible will be obtained. The primary reason for termination or discontinuation will be documented on the Study Exit Form. Study subjects will be discontinued from the study if their stone could not be accurately assessed on the CT image. This subject would be considered a screen failure. Subjects who prematurely discontinue the study or are withdrawn from the study by the investigator after they receive general anesthesia will not be replaced.

Anticipated reasons for early termination of subject participation include:

- Subject Lost to Follow-Up: Unable to locate subject despite at least three documented attempts to notify the subject via telephone or e-mail, and by certified mail. A subject will not be considered lost to follow-up until the last scheduled follow-up visit (30 day follow up visit or 90 day follow up visit if subject has unresolved hydronephrosis).
- Subject's Withdrawal of Consent: The subject requests to terminate his/her involvement in the study, therefore withdrawing his/her consent to participate in the study (the investigator must thoroughly document the reasons for termination). Attempts will be made to retrieve any follow-up data, prior to the time point at which voluntary consent was withdrawn, when available, in particular regarding possible adverse events (AEs) at the time of study discontinuation.
- Subject Withdrawn by Investigator: Subjects who are withdrawn by the Investigator for any reason prior to study completion.
- Subject Death: If possible, an autopsy and/or death certificate should be obtained in order to document the cause of death.

Any subjects discontinued prior to receiving general anesthesia will be classified as screen failures and exited from the study and will not be included in any endpoint analysis.

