- Subject's usage of all prescription medications (type, dose, and frequency) will be documented. In addition, any non-prescription medication (type, dose, and frequency) that may impact stone disease, acting as stone formation promoters (e.g., calcium or ascorbic acid) or stone formation inhibitors (e.g., magnesium or citric acid) will also be documented, whether such medications were taken in connection with the scheduled study procedure or otherwise.

8.2. Study Treatment – Investigational Arm and Control Arm

The investigator and designated co-investigator(s) will be trained to the Acoustic Enhancer Instructions for Use (IFU) before performing the investigational procedure.

On the day of the procedure and prior to randomization, the investigator will verify:

- If urinalysis is more than 7 days removed from the procedure, a negative urinalysis, with an absence of UTI symptoms, should be obtained on the day of the procedure.
- Female subjects are not pregnant using urine or serum testing.

The subject will be placed under general anesthesia and positioned following standard procedures for URS-LL. The investigational procedure involves the use of Acoustic Enhancer to augment the URS-LL that is done per standard practice. Procedures will be performed by the investigator (PI) and/or designated sub-investigator(s).

To facilitate reliable comparisons of treatment success between the Acoustic Enhancer with URS-LL (investigational arm) and URS Laser Lithotripsy (control arm), technique and equipment will be standardized as follows for all procedures:

- Ho:YAG lasers approved for ureteroscopic laser lithotripsy (30W to 120W) will be used
 - Moses mode or Thulium laser equipment is **NOT ALLOWED**
- Laser fibers of < 300µ diameter will be used.
- At investigator's discretion, ureteral access sheaths (10-16Fr outer diameter) may be used.

- Laser setting at 0.2 J to 1.5J, (**DO NOT** exceed 1.5J), frequency 5 Hz to 60 Hz.
 - **DO NOT** exceed a time-averaged power of 25 W (the product of the pulse energy and pulse repetition rate at any point during the procedure).
- A flexible ureteroscope (disposable or non-disposable) will be used; no semi-rigid ureteroscopes are allowed for the laser lithotripsy portion of the procedure.
- Use standard irrigation. To prevent unintentional suctioning of the Acoustic Enhancer microbubbles, **DO NOT** use continuous suction devices (e.g., ClearPetra, LithAssist).

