10.2. Analysis Population

The study results will be summarized based on three populations:

Intent-to-Treat (ITT): The ITT population consists of all randomized subjects who meet the study inclusion/exclusion criteria. Subjects who develop UTI or having their stone move to the middle/distal ureter between the time they were screened and were found to be eligible at the time they were randomized, or who no longer meet any of the other inclusion/exclusion criteria at the time of the procedure, will not be treated under the protocol. These subjects will not be included in the ITT analysis. The ITT population will be used for all effectiveness analyses with groups based on the randomized treatment.

Safety Population: The Safety population consists of all subjects who had a procedure performed. The Safety population will be used for the safety summaries (adverse events or strictures) with groups based on the actual treatment received.

CONFIDENTIAL Page 32 of 53

Acoustic Enhancer Research on Laser Lithotripsy (AEROLITH) Clinical Study

Per-Protocol Population (PP): The Per-Protocol population will consist of all subjects who complete the primary endpoint information without a major protocol deviation; PP will include subjects who have evaluable CTs both at baseline and at 30-day follow-up. The PP population analyses will be completed based on the randomized treatment arm.

The definition of major protocol deviations will be defined prior to any final analysis. Subjects who are screened but not randomized will not be included in analysis. Any information on these subjects will be made available in a listing if requested by the IRB or FDA.

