11.2. Device Malfunction

For the purposes of this protocol, a device malfunction is defined as the failure of a device to meet its performance specifications or otherwise perform as intended [21CFR803.3(k)]. Examples of a device malfunction include breached packaging, broken Acoustic Enhancer vials.

All device malfunctions must be reported to the Sponsor and entered in the EDC within 24 hours of the knowledge.

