В	DCO-243	15 APR 2021	 Section 5.8 and protocol synopsis section: An exclusion criterion of "Patients who have had prior URS-LL within 3 months on the side to be treated at the time of consent" is added to minimize/prevent confounding clinical outcomes in the analysis of data. Section 5.8 and protocol synopsis section: Exclusion criterion "If female, last menstrual cycle(s) is >30 days on the study procedure unless patient has a documented history of menstrual cycle(s) that are absent or are >30days if not pregnant" is removed since all females will be required to take a pregnancy test on the day of the procedure. Protocol Synopsis section: Added Abond CRO, Inc. information. Abond CRO will be responsible for managing the AEROLITH study's data and conducting statistical analysis. Section 5.5: added the words "and randomized" and "subjects" for clarity. This language, added for clarity, is consistent with the language in the original IDE protocol. Section 6.3.2: Reworded section to "Re-interventional procedure(s) on stone(s) that were treated as part of the AEROLITH study" for clarity. Section 6.4.2 "Subjects will be blinded of their treatment allocation through index procedure" was added as a measure to minimize bias. Section 7.3: Changed the timing of randomization from after subject receives general anesthesia to randomizing a subject the day of the procedure. The rationale for this change is to minimize logistical challenges of unnecessarily transporting temperature sensitive investigational devices to the Operating Room (OR) if it's not needed. Further, this minimizes or prevents an incident of not being able to secure a randomization number from the EDC if the OR does not have a computer or Wifi connectivity. To maintain the scientific soundness of the study, subjects will still be blinded of their treatment allocation through index procedure. Section 7.5: added subject identification coding system. Sections 8.5. A

CIP-0001(E) Acoustic Enhancer Research on Laser Lithotripsy (AEROLITH) Clinical Study DCO-326 EFFECTIVE DATE: 19 JAN 2022

> **CONFIDENTIAL** Page 50 of 53

·  	-	Acoustic Enhancer Research on Laser Lithotripsy (AEROLITH) Clinical Study				

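### Protocol 7.6 and the ITT definition in Protocol 10.2 and SAP 6.1.1 give opposite answers for an eligible subject who is randomized and then stopped before anesthesia, and neither document says which governs

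*Protocol*

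**What the plan says.** **Protocol 7.6 (Subject Withdrawal or Discontinuation).** "Any subjects discontinued prior to receiving general anesthesia will be classified as screen failures and exited from the study and will not be included". That exclusion applies to every endpoint analysis. The sentence has no exception for subjects already randomized and no limit on the reason. The same section says that subjects who stop or are withdrawn "after they receive general anesthesia will not be replaced". It also makes a subject a screen failure when the stone cannot be accurately assessed on CT, without saying which CT.

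**Protocol 10.2 and SAP 6.1.1.** "The ITT population consists of all randomized subjects who meet the study inclusion/exclusion criteria". Both then remove subjects who no longer meet the criteria at the time of the procedure. Neither mentions anesthesia.

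**Protocol 7.3.** After consent and eligibility, "the subject will be randomly assigned to the investigational or control arm on the day of the procedure". No anesthesia condition is attached.

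**Protocol 8.2.** Checks to be made before randomization come first. The text then continues: "The subject will be placed under general anesthesia and positioned following standard procedures for URS-LL".

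**Protocol 7.4.** Two parties are blinded: the subject, through the index procedure, and the independent CT reader.

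**Protocol 10.4 and 10.6.** The primary test uses the ITT set with multiple imputation, by treatment group. A tipping-point analysis covers unavailable ITT responses.

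**The concern.** The anesthesia cut-off in 7.6 would be harmless if randomization followed anesthesia, because everyone removed would be unrandomized. Under the current order it falls after allocation. The Rev B entry in the revision history, used here only as background, suggests how this arose: "Changed the timing of randomization from after subject receives general anesthesia to randomizing a subject the day of the procedure". Its reason was to "minimize logistical challenges of unnecessarily transporting temperature sensitive investigational devices to the Operating Room" when the device is not needed, which implies that site staff can know the arm before the subject reaches the operating room.

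If 7.6 is followed at database lock, an eligible subject can leave the primary set after allocation by the decision of people who may know the arm. That subject is then not a missing outcome: neither the imputation nor the tipping-point analysis sees the case. The superiority test would compare groups open to selection after randomization, under the name ITT. If 10.2 is followed instead, none of this happens. The choice should not be left until lock.

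**Working it through.** **1. The rules side by side, for an eligible subject, randomized and then stopped before anesthesia**

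| Source | Status |
|---|---|
| Protocol 10.2, SAP 6.1.1 | In ITT, in the randomized arm |
| Protocol 10.4, 10.6 | Outcome missing: imputed and included in the tipping-point analysis |
| Protocol 7.6 | Screen failure, in no endpoint analysis |
| SAP 2, SAP 6.1.2 | Exclusions after randomization cover only subjects who fail eligibility, so they do not apply |
| SAP 13 | Lists one change from the protocol, on a different matter |

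No section ranks these rules. SAP 5 and 8 defer the primary analysis to a separate plan that is not among the documents.

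**2. The plan's own figures (Protocol 10.3)**

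Inputs: 55% and 75%, one-sided 0.025, 88 per arm. With a zero margin the Farrington-Manning test is the pooled-variance z test. Its power is 0.7996 by the normal approximation and 0.803 by exact enumeration of two binomials. Inflation: 176 / 0.90 = 195.6, hence 196 (98 per arm). The design reproduces. No stated figure is wrong.

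**3. Illustration of the effect if 7.6 governs**

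Assumptions, none of them from the documents: *k* of 98 subjects are dropped from the investigational arm only, and their success chance would have been *q*. The true rate is 55% in both arms.

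Rate among those retained = (98 × 0.55 − *kq*) / (98 − *k*) = (53.9 − *kq*) / (98 − *k*).

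Type I error is by exact enumeration of the pooled z test, 98 − *k* against 98.

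| *k* | *q* | Retained rate | Bias (points) | Type I error |
|---|---|---|---|---|
| 0 | – | 0.550 | 0 | 2.6% |
| 2 | 0.30 | 53.3/96 = 0.555 | 0.5 | 2.9% |
| 2 | 0 | 53.9/96 = 0.561 | 1.1 | 3.6% |
| 4 | 0.30 | 52.7/94 = 0.561 | 1.1 | 3.4% |
| 4 | 0 | 53.9/94 = 0.573 | 2.3 | 5.0% |

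With *q* = 0.55 the retained rate stays at 0.55 and there is no bias for any *k*. For scale, the standard error of the difference is √(2 × 0.55 × 0.45 / 98) = 0.071, about 7 points.

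**4. What keeping the subjects changes**

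The same scenarios were simulated with the *k* subjects kept in ITT, no CT, and 50 by-arm imputations. Stone covariates were left out, which is a simplification. At *k* = 4 the type I error was about 3.5% (*q* = 0.30) and about 5% (*q* = 0), the same as under deletion to within simulation error. By-arm imputation gives each subject the success rate of those retained in the arm, so it cannot correct for a difference between the two groups. Only a CT actually obtained, or the tipping-point analysis, can show it.

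**The case against.** A reader might infer that eligible subjects will be deleted by people who know the arm, that the error rate is therefore inflated, and that retaining the subjects cures it. The documents do not support that chain.

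- **Deletion is not settled.** It follows only if 7.6 governs. The SAP repeats the 10.2 definition, applies ITT to all effectiveness analyses and contains no anesthesia rule.
- **Knowledge of the arm is partial.** It is inferred for site staff from the blinding section. A subject who withdraws unprompted is blinded. In 7.6 the investigator's permission to withdraw a subject is limited to reasons unrelated to study treatment and in the subject's best medical interest. The order of randomization before anesthesia is itself implied rather than stated.
- **The obvious arm-specific event does not establish bias.** Protocol 11.2 says: "Examples of a device malfunction include breached packaging, broken Acoustic Enhancer vials". That can happen only in the investigational arm, but a damaged vial has no evident link to stone prognosis. Section 11.2 requires a report and does not mention discontinuation. Under Protocol 2.1 the material is prepared immediately before use, so a defect may come to light after anesthesia.
- **The size is assumed.** The window is part of one day. One subject dropped with a 30% success chance gives 2.65% against a baseline of 2.62%.
- **Visibility is largely provided.** SAP 6.2 and Tables 14.0.1 and 14.0.2 report randomized-but-untreated subjects and population exclusions, with reasons, by arm.

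All of this stands, and it limits the point to the conflict itself. It does not remove the conflict: a disposition table does not return a subject to the primary analysis or the tipping-point analysis.

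**Conclusion.** The conflict is real in the current text. For an eligible subject randomized and then stopped before anesthesia, Protocol 7.6 and Protocol 10.2 (with SAP 6.1.1) cannot both be followed. As written, 7.6 permits eligible subjects to leave the primary set after allocation.

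Its effect is unknown and probably small. The illustrated type I error of 2.9–3.6% at two subjects and 3.4–5.0% at four rests on one-sided loss and on success chances of 30% to 0% among those lost, none of which the documents support as a forecast. If those lost are average for their arm, there is no bias. These rates should not be quoted as an inflation that the correction removes, because by-arm imputation without a CT leaves them essentially where they were. The case for correction is that the ITT set is protected from selection after randomization, that any CT obtained counts, and that the remaining subjects enter the tipping-point analysis. The correction should be made before lock because it costs almost nothing.

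**What to change.** In Protocol 7.6:

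1. Move the cut-off in the screen-failure sentence from anesthesia to randomization.
2. State that an eligible randomized subject discontinued before anesthesia stays in ITT in the randomized arm. Use any follow-up CT, timed from the randomization or planned procedure date if no procedure took place, since the endpoint is otherwise anchored to the index procedure. Without a CT the outcome is missing and goes to the 10.6 imputation and tipping-point analysis.
3. Align the replacement sentence to the same randomization cut-off, so that a retained subject is not also replaced.
4. Say that the sentence on stones not accurately assessable on CT refers to the baseline CT read before randomization. As it stands it could be read to cover a 30-day CT, whereas evaluable CTs are a condition of the per-protocol set only (10.2) and missing outcomes in ITT are imputed (10.4).

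SAP 6.1.1 already carries the ITT definition, so a clarifying line there is optional. The separate primary-analysis plan should follow the same rule. No new by-arm table is needed.

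Cost: a few sentences, and perhaps a few more missing outcomes in the primary set. No visit, treatment or sample-size figure changes.

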8. SUBJECT ASSESSMENT AND STUDY VISIT SCHEDULE AND PROCEDURES

8.1. Pre-Treatment Visit

After the subject has completed the informed consent process, research staff will review potential subject's medical history, including available images, to verify study subject's eligibility. In addition, research staff will conduct protocol required assessments prior to the index procedure to obtain baseline information and verify subject eligibility.

- As part of routine care, study subjects may be prescribed medications such as analgesics, alpha blockers, calcium channel blockers, antibiotics to take as needed.
- Research staff will review subject's medical history, including available images, to verify study eligibility.
- Subjects will complete a baseline health status and undergo focused urogenital calculus physical exam and vital signs.

- Subjects will undergo a CT scan to measure stone dimensions (in mm), and location (e.g., the upper (superior) pole, lower (inferior) pole, and interpolar region of the kidney, pelvis of the kidney, and proximal ureter). This will be noted on the Electronic Case Report Form (eCRF). If there are multiple stones, each one will need to be measured and its location (i.e., pelvis, ureter), size will be documented.
 - CT image acquisition parameters will follow CLIN-0002: Image Acquisition Protocol, AEROLITH Study. A CT image collected prior to screening may be used as baseline CT image. The CT image will be used to measure stone size and the location of the stone.
 - Measuring baseline stone size(s) will be conducted by the investigator following CLIN- 0003: Radiographic Evaluation Protocol of Applaud's Acoustic Enhancer with Laser Lithotripsy System in the Treatment of Urinary Stones
 - A Stone Size Measurement Verification Electronic Case Report Form (eCRF) will be completed by the investigational site and the baseline CT image will be uploaded to the core lab for analysis following CLIN-0003.
- Subjects will undergo a urinalysis to verify absence of Urinary Tract Infection (UTI) and verify pH level is ≥ 5.5. *Note:* If a patient's largest stone intensity is ≥ 500HU and has a historical pH value of ≥ 5.5, a recently tested (within 30 days of consent) urine pH showing <5.5 in this case is acceptable.
- Serum creatinine to verify renal function and serum creatinine is < 1.5mg/dl.
- Subject's usage of all prescription medications (type, dose, and frequency) will be documented. In addition, any non-prescription medication (type, dose, and frequency) that may impact stone disease, acting as stone formation promoters (e.g., calcium or ascorbic acid) or stone formation inhibitors (e.g., magnesium or citric acid) will also be documented, whether such medications were taken in connection with the scheduled study procedure or otherwise.

8.2. Study Treatment – Investigational Arm and Control Arm

The investigator and designated co-investigator(s) will be trained to the Acoustic Enhancer Instructions for Use (IFU) before performing the investigational procedure.

On the day of the procedure and prior to randomization, the investigator will verify:

- If urinalysis is more than 7 days removed from the procedure, a negative urinalysis, with an absence of UTI symptoms, should be obtained on the day of the procedure.
- Female subjects are not pregnant using urine or serum testing.

The subject will be placed under general anesthesia and positioned following standard procedures for URS-LL. The investigational procedure involves the use of Acoustic Enhancer to augment the URS-LL that is done per standard practice. Procedures will be performed by the investigator (PI) and/or designated sub-investigator(s).

To facilitate reliable comparisons of treatment success between the Acoustic Enhancer with URS-LL (investigational arm) and URS Laser Lithotripsy (control arm), technique and equipment will be standardized as follows for all procedures:

- Ho:YAG lasers approved for ureteroscopic laser lithotripsy (30W to 120W) will be used
 - Moses mode or Thulium laser equipment is **NOT ALLOWED**
- Laser fibers of < 300µ diameter will be used.
- At investigator's discretion, ureteral access sheaths (10-16Fr outer diameter) may be used.

- Laser setting at 0.2 J to 1.5J, (**DO NOT** exceed 1.5J), frequency 5 Hz to 60 Hz.
 - **DO NOT** exceed a time-averaged power of 25 W (the product of the pulse energy and pulse repetition rate at any point during the procedure).
- A flexible ureteroscope (disposable or non-disposable) will be used; no semi-rigid ureteroscopes are allowed for the laser lithotripsy portion of the procedure.
- Use standard irrigation. To prevent unintentional suctioning of the Acoustic Enhancer microbubbles, **DO NOT** use continuous suction devices (e.g., ClearPetra, LithAssist).
- If possible, perform retrograde stone displacement into the pelvis/calyx following institution standard protocol.

During laser lithotripsy, small volumes of Acoustic Enhancer are placed in the urine near the stone at periodic intervals (refer to the IFU).

Lasering is continued until any visible remaining fragments are estimated to be 1-2 mm in size or smaller.

For the purposes of this study, no basketing will be performed for stone retrieval. If basketing is performed, this will be captured and recorded as a major protocol deviation. No other concomitant procedures, including diagnostic procedures, are allowed during the treatment. Any concomitant procedure (i.e., basketing) being conducted will be documented as a major protocol deviation.

Post-treatment, ureteral stents will be placed in all subjects for 3 to 14 days. If a stent cannot be placed, this will be captured and recorded as a minor protocol deviation.

Investigators must record any stents remaining >14 days post procedure and document any observations of calcification or encrustation. If a stent is removed outside of the window (3-14 days), this will be captured and recorded as a minor protocol deviation. If calcification and/or encrustation is observed, an Adverse Event CRF should be completed.

Document any adverse events observed during the procedure (see Adverse Events section below).

8.3. Recovery and Discharge

Recovery and discharge procedures will follow standard protocol at the treating institution. Any adverse events will be documented.

8.4. Follow up call at Day 14 (14 days +/- 4 days after each procedure)

- Conduct a follow-up call after the treatment.
- Document any reported AEs since last observation was performed (see Adverse Events section below).
- If symptoms of Urinary Tract Infection (UTI) are reported by subjects, conduct a urinalysis and subsequent urine culture if clinically indicated to verify presence/absence of UTI.
- Document all prescription medications. In addition, document any non-prescription medication that may impact stone disease, acting as stone formation promoters (e.g., calcium or ascorbic acid) or stone formation inhibitors (e.g., magnesium or citric acid).
- Record date of stent removal in the 14-day Follow Up Evaluation CRF

Note: If a stent is removed at >14 days but <30 or <90 days post procedure, please complete Follow Up (On-site) Evaluation CRF and select unscheduled visit for visit type.

8.5. 30-day follow-up (30 +14 days after procedure)

- Conduct focused urogenital calculus physical exam and vital signs.
- Measure serum creatinine to assess renal function.
- Document any reported AEs since last visit (see Adverse Events section below)
- If symptoms of Urinary Tract Infection (UTI) are reported by subjects, conduct a urinalysis and subsequent urine culture if clinically indicated to verify presence/absence of UTI.
- Document all prescription medications. In addition, document any non-prescription medication that may impact stone disease, acting as stone formation promoters (e.g., calcium or ascorbic acid) or stone formation inhibitors (e.g., magnesium or citric acid)
- Conduct CT imaging following acquisition parameters delineated in CLIN-0002: Image Acquisition Protocol, AEROLITH Study
 - **Note 1:** As presence of ureteral stents may obscure image analysis, remove stents from the treated kidney/ureter prior to collecting the CT images.
 - **Note 2:** If a stent is removed outside of the window (3-14 days post procedure), this will be captured and documented using Protocol Deviation CRF as minor protocol deviation.
 - Note 3: If a stent is removed at >14 days, verify absence or presence of calcification and/or encrustation via standard of care imaging (e.g., KUB X-ray). If calcification and/or encrustation is observed, complete Adverse Event CRF.
- Upload the CT images to the core lab for analysis.
- Complete Study Exit CRF
 - **Note 1:** For those subjects with new or on-going device and/or procedure-related serious adverse events at 30 days post procedure, they will be followed until the event has resolved or is deemed stable by the investigator.
 - **Note 2:** For those subjects with new or on-going device and/or procedure related hydronephrosis and those subjects with pre-existing (prior to treatment) hydronephrosis that have worsened or recurred since baseline, they will be followed through 90-days post procedure (see below).

8.6. 90-day follow-up and Study exit (90 +/- 21 days after last treatment) only for those subjects with new and unresolved device and/or procedure related hydronephrosis and subjects with pre-existing (prior to treatment) hydronephrosis that have worsened or recurred at 30 days

- Conduct focused urogenital calculus physical exam and vital signs.
- Document any reported AEs since last visit (see Adverse Events section below).
- If symptoms of Urinary Tract Infection (UTI) are reported by subjects, conduct a urinalysis and subsequent urine culture if clinically indicated to verify presence/absence of UTI.
- Document all prescription medications. In addition, document any non-prescription medication that may impact stone disease, acting as stone formation promoters (e.g. calcium or ascorbic acid) or stone formation inhibitors (e.g. magnesium or citric acid).
- Perform diagnostic renal-bladder ultrasound to verify presence/absence of hydronephrosis.

- Complete Study Exit CRF
 - Note 1: For those subjects with on-going device and/or procedure-related serious adverse events (including device and/or procedure-related hydronephrosis and worsening/recurring hydronephrosis from baseline) at 90 days post procedure, they will be followed until the event has resolved or is deemed stable by the investigator. For subjects with on-going, including stable, device and/or procedure-related serious adverse events (including device and/or procedure-related hydronephrosis from baseline) at 90-days post procedure, the investigator should refer the subject for further care to the subject's primary care provider or urological specialist upon exiting the study.

Table 2: Schedule of Events Table

Study Visit Day	Screening	Treatment	Day 14 (+/- 4 days) after procedure	Day 30 (+14 days) after procedure	Day 90 (+/- 21 days) after procedure ***
Informed Consent	Х				
Patient Eligibility Review	Х				
Medical History	Х				
Phone Call			Х		
Site Visit	Х	х		х	Х
Urine or serum pregnancy test		X+			
Focused Urogenital Calculus Physical Exam and Vital Signs	x			х	х
Serum creatinine	Х			х	
Urinalysis	x		 X Urinalysis if symptomatic for UTI Urine culture if clinically indicated 	 X Urinalysis if symptomatic for UTI Urine culture if clinically indicated 	 X Urinalysis if symptomatic for UTI Urine culture if clinically indicated
CT scan (non-contrast) stone presence, size & location	X*			X**	
Treatment: Investigational or Control Arm		x			
Ultrasound (renal bladder)					Х
Other Assessments					
Adverse Event		x	Х	х	х
Concomitant Prescription Medications. In addition, any non-prescription medication that may impact stone disease, acting as stone formation promoters (e.g., calcium or ascorbic acid) or stone formation inhibitors	x	x	х	x	х
(e.g. magnesium or citric acid). Protocol Deviation (if appropriate)	x	x	X	x	X

*CT within 60 days of subject signing consent. If CT imaging has not been conducted yet for the patient, please follow CT image acquisition parameters detailed in CLIN-0002.

Stone measurement will follow the Radiographic Evaluation Protocol of Applaud Medical's Acoustic Enhancer with Laser Lithotripsy System in the Urinary Treatment of Stones (Doc. No. CLIN-0003)

⁺ Pregnancy test to be done on the day of treatment prior to randomization

** See Imaging Acquisition Protocol, Acoustic Enhancer Research in Laser Lithotripsy (Doc. No. CLIN-0002)

***Only those subjects who have unresolved hydronephrosis at 30 days post-procedure.

